## **9. STATISTICAL CONSIDERATIONS**

### **9.1. Sample Size Determination**

The sample size of 46 was estimated for 95% confidence interval based on a standard deviation of 5 seconds and target distance from mean to limits of 1.5 seconds (PASS-Confidence Intervals for One Mean). Results from a previous study conducted by Ecolab (summarized in the Appendix) was utilized as a starting point sample size estimation for the current protocol, using PASS 2021 Power Analysis and Sample Size Software (2021). NCSS, LLC. Kaysville, Utah, USA, [ncss.com/software/pass](http://ncss.com/software/pass). In the event that a participant withdraws from the study, additional participants will be enrolled to achieve a final number of 46 participants with complete data and until adequate power for analysis has been reached.

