### **9.3. Populations for Analyses**

The analyses will be performed on the intent to treat (ITT) population which consists of all subjects who participated in the study, meaning they have full data on all covariates as well as the hand sanitizer dry time.

No per protocol, safety, or other analyses groups are planned.

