### **9.6. Demographics, Variables and Covariates**

Age will be collected as a continuous measure, with all participants being  $\geq 18$  years of age. Age strata will be defined as stratum 1: 18-25 years old, stratum 2: 26-41 years old, stratum 3: 42-57 years old, stratum 4: 58-67 years old, stratum 5: 68-76 years old, stratum 6: 77-94 years old, 95+ years old. Age will be considered for secondary analysis.

Sex will be collected as a categorical equal to 0=male, 1=female, or 2=other. Sex will be considered for secondary analysis.

Hand size will be calculated using the formula  $2.48 \times \text{hand length} \times \text{hand breadth}$  as described by (Wilkinson et al. (2017), Bellissimo-Rodrigues et al. (2015) and Hsu and Yu (2010)).

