## **9.8. Statistical Analysis**

Statistical analyses will be conducted in SAS® software, Version 9.4 or higher of the SAS System for Windows (Copyright © 2013 SAS Institute Inc.) or other appropriate statistical software.  $P < 0.05$  will be considered statistically significant.

All continuous variables will be summarized using the following descriptive statistics: (non-missing sample size), mean, standard deviation, median, maximum and minimum. The frequency and percentages (based on the non-missing sample size) of observed levels will be reported for all categorical measures. 95% confidence intervals will be calculated for all means.

A box-and-whisker plot will be employed to display the mean, interquartile range, range, and any possible outliers for wet-to-dry time.

Spearman correlation analysis will be used to examine possible associations between the key variable of dry time with age, sex, and hand size. Additional t-tests or non-parametric tests will be employed to further examine any significant associations found in the correlational analyses between key and covariate measures.

If the results of the interim analysis of 46 participants on the medium dispenser setting (1.0 mL) does not demonstrate that hands stay sufficiently stay wet for at an average of at least 15 seconds, a second data collection whereby another 46 participants will undergo the study using the high dispenser setting (1.4 mL) will take place. All analyses presented above would then be repeated for the data from an additional 46 participants at the high dispenser setting (1.4 mL).

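### Section 9.8 yields a covariate effect in seconds only after that covariate passes P<0.05, so those estimates are inflated by selection (minor point)

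*Combined protocol and SAP*

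**What the plan says.** The first step in section 9.8 is unconditional: "Spearman correlation analysis will be used to examine possible associations between the key variable of dry time with age, sex, and hand size". In the same section P<0.05 "will be considered statistically significant"; neither sidedness nor any multiplicity adjustment is given. The second step is conditional: "Additional t-tests or non-parametric tests will be employed to further examine any significant associations found in the correlational analyses".

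Section 9.3 defines one analysis set: "The analyses will be performed on the intent to treat (ITT) population which consists of all subjects who participated in the study". There is no hold-out sample, so both steps use the same people.

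Section 9.6 says "Age will be collected as a continuous measure, with all participants being" at least 18 years old. It lists age bands, codes sex in three categories and computes hand size from length and breadth. It marks age and sex for secondary analysis, while section 9.5.2 lists no secondary endpoint. No grouping is given for hand size, and section 9.8 does not link the age bands to the follow-up tests.

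If the 1.4 mL stage runs, the same procedure applies there: "All analyses presented above would then be repeated for the data from an additional 46 participants at the high dispenser setting".

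**The concern.** A Spearman coefficient shows whether wet time rises or falls with a covariate, but not by how many seconds. Under section 9.8 the figure in seconds comes from the follow-up comparison, and that comparison is made only when the correlation in the same data is large enough to be significant. With 46 participants this favours samples in which chance has enlarged the association. The differences that reach the report are then too large on average, and their confidence intervals do not have the nominal coverage.

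Two further points follow. A significant follow-up test adds little, because it is computed from the values that triggered it. For hand size, and possibly for age, the groups could be chosen after the correlation has been seen. At stake is how a reader judges the influence of hand size, sex or age on wet time.

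**Working it through.** **Inputs from the documents.** N = 46, SD 5 s, half-width 1.5 s, 95% CI (section 9.1); threshold P<0.05 and the two-step rule (9.8); one analysis set (9.3).

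**Assumptions.** Two-sided tests; normal data; 23 participants per sex; true sex difference 1.5, 2.5 or 4 s; correlation 0.2, 0.3 or 0.4 with a continuous covariate; median split as the follow-up grouping. None of these is in the documents.

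**The plan's own figure.** Section 9.1 states: "The sample size of 46 was estimated for 95% confidence interval based on a standard deviation of 5 seconds", with a "target distance from mean to limits of 1.5 seconds". The smallest n with t(0.975, n−1) × 5/√n ≤ 1.5 is 46: 2.014 × 5/√46 = 1.485 s. The figure reproduces. It sizes the study for one mean; no sample size or power is given for the covariate analyses.

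**How large an association must be to pass.** With t(0.975, 44) = 2.015, the critical correlation is 2.015/√(44 + 2.015²) = 0.29. On the seconds scale for sex, the standard error of a difference is 5 × √(2/23) = 1.47 s, so a t-test needs about 2.015 × 1.47 = 2.97 s. A true difference of 1.5 s is therefore unlikely to be followed up unless the sample roughly doubles it.

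**Simulation, sex (40,000 trials per setting; Spearman P<0.05, then a t-test on the same data).**

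| True difference | Followed up | Mean difference when followed up | Ratio |
|---|---|---|---|
| 1.5 s | 16% | 3.56 s | 3.56/1.5 = 2.4 |
| 2.5 s | 37% | 3.94 s | 3.94/2.5 = 1.6 |
| 4 s | 74% | 4.62 s | 4.62/4 = 1.16 |

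**Simulation, continuous covariate with median split.**

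| True correlation | Followed up | Ratio of followed-up to true difference |
|---|---|---|
| 0.2 | 24.5% | 1.99 |
| 0.3 | 49.1% | 1.41 |
| 0.4 | 75.3% | 1.16 |

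At correlation 0.3 the mean split difference is 0.470 SD over all trials and 0.669 SD over followed-up trials. With SD 5 s that is 0.470 × 5 = 2.4 s against 0.669 × 5 = 3.3 s.

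**Is the second test new evidence?** With no true association, the follow-up t-test has P<0.05 in 81% (sex) or 50% (median split) of the cases that reach it; a test on independent data would give 5%. For two-level sex, Spearman is essentially the rank-sum test, so a non-parametric follow-up would repeat it.

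**False positives at the first step.** Three independent tests at 0.05 give 1 − 0.95³ = 14.3%. Simulation gives 14.2%, or 13.4% when hand size is related to sex.

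**Effect of removing the condition.** Without the significance gate, the mean estimated sex differences are 1.49, 2.50 and 4.00 s for true values of 1.5, 2.5 and 4 s, and the 95% CIs cover the truth in about 95% of trials. Among followed-up cases, coverage is 84% at a true difference of 1.5 s and 19% when there is no difference.

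**The case against.** The strongest reply is that these are secondary, descriptive analyses written in cautious terms, and much of it stands.

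- A reader might infer that non-significant covariates get no estimate. The documents do not support that: all three correlations are planned without a significance condition, and nothing limits reporting to the significant ones. What is missing is an estimate in seconds.
- A reader might infer that the plan offers the second test as confirmation. It does not; it speaks only of examining associations further. The 81% and 50% figures show why such a reading would be wrong, not that the plan makes it.
- The follow-up is not confined to t-tests. A male–female comparison needs no cut, and a multi-group rank test could use the age bands. A grouping chosen after the fact is a clear gap for hand size and only a possible one for age.
- The second step costs no power to detect an association, because Spearman is run first on ungrouped values. Nor does it add false positives: with no association, the chance of passing both steps is about 0.050 × 0.50 = 2.5% for a median split.
- The size of the inflation depends on assumed effects and, for continuous covariates, on an assumed split. It is small when the true effect is large.

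None of this removes the selection: the planned difference in seconds remains conditional on significance in the same data.

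**Conclusion.** The point holds as a minor one. Section 9.8 makes the covariate effect in seconds available only after significance in the same participants, so that estimate is biased away from zero. Under the assumptions above, the factor is about 1.2 to 2.4 for sex and about 1.2 to 2.0 for a median split, and smaller true effects are inflated more. The three Spearman coefficients, taken as a full set, are not selected.

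It would be tempting to read this as a threat to the trial's conclusion. The documents do not support that: the primary mean wet time, its confidence interval, the N of 46 and the 15-second decision do not depend on the covariate step.

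**What to change.** Replace the significance-triggered follow-up in section 9.8 with one prespecified estimate and 95% CI per covariate, reported whatever its P value, alongside the three Spearman coefficients. One suitable form is:

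- a male–female difference in seconds, with any participants in the third sex category described separately;
- a slope in seconds for age, kept continuous;
- a slope in seconds for hand size, kept continuous.

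The units are the sponsor's choice, provided that they are fixed in advance. If the age bands are shown, use them descriptively. Label these analyses exploratory, because reporting every estimate removes the selection bias but leaves the chance of about 14% of at least one false positive among three unadjusted tests. Apply the same wording to the 1.4 mL cohort if it is enrolled.

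The cost is SAP wording only: age, sex and hand size are already collected, and no participants or procedures are added. The downside is that the slopes assume approximate linearity, which should be checked with a plot.

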## 10. SUPPORTING DOCUMENTATION AND OPERATIONAL CONSIDERATIONS

### a. Regulatory and Ethical Considerations

#### i. Confidentiality and Privacy

Participant confidentiality and privacy is strictly held in trust by the PI and the staff. Therefore, documentation, data, and all other information generated will be held in strict confidence. No information concerning the study or the data will be released to any unauthorized third party without prior written approval of the PI. All study data and study records will be managed and stored in accordance with the site's policies on data storage and security. All electronic transmission of data will adhere to Health Insurance Portability and Accountability Act (HIPAA) and any local regulations.

Representatives of the IRB, and regulatory agencies may inspect all documents and records required to be maintained by the PI, including but not limited to, medical records (office, clinic, or hospital) and pharmacy records for the participants in this study. The clinical study site will permit access to such records.

A master list linking participant numbers to patient name and medical record number will be maintained in a secure database by the PI or paper files in secure cabinet(s). The study participant's contact information will be securely stored at each clinical site for internal use during the study. The PI will agree to notify the IRB of any intent to move or destroy these documents.

#### ii. Study Discontinuation

This study may be temporarily suspended or prematurely terminated if there is sufficient reasonable cause. Written notification, documenting the reason for study suspension or termination, will be provided by the suspending or terminating party to the PI and IRB. If the study is prematurely terminated or suspended, the PI will promptly inform the IRB and will provide the reason(s) for the termination or suspension.

Circumstance(s) that may warrant termination or suspension include, but are not limited to:

- Determination of unexpected, significant, or unacceptable risk to participants as determined by AE review

The study may resume once concerns about safety, protocol compliance, and data quality are addressed, and the IRB is satisfied.

#### iii. Data Handling and Record Keeping

Data collection is the responsibility of the study staff at the site under the supervision of the PI. The PI is responsible for ensuring the accuracy, completeness, legibility, and timeliness of the data reported in the CRFs or any other study activity documentation as

part of this study. All the documents should be completed in accordance with Good Documentation Practices (GDP) to ensure accurate interpretation of data.

Final storage of Medline data will be per ICH/GCP guidelines and kept stored in a protected access area for the length of the time required.

iv. Conflict of Interest Policy

The independence of this study from any actual or perceived influence is critical. Therefore, any actual conflict of interest of persons who have a role in the design, conduct, analysis, publication, or any aspect of this trial will be disclosed and managed.

**b. Protocol Deviations**

It is the responsibility of the PI and study staff to use continuous vigilance to identify and report deviations on a routine basis. All deviations must be addressed in the study source documents, and reported to Medline Industries, LP. Protocol deviations must be sent to the reviewing IRB per reporting requirements in a timely manner. The PI is responsible for knowing and adhering to the reviewing IRB requirements.

**c. Abbreviations**

AE	Adverse Event
CDC	Centers for Disease Control and Prevention
CFR	Code of Federal Regulations
CRA	Clinical Research Associate
CRF	Case Report Form
CRO	Contract Research Organization
FDA	Food and Drug Administration
GCP	Good Clinical Practice
GDP	Good Documentation Practice
HIPAA	Health Insurance Portability and Accountability Act
ICH	International Conference on Harmonization
IRB	Institutional Review Board
PI	Principal Investigator

SAE	Serious Adverse Events
SOA	Schedule of Activities
U.S.	United States
WHO	World Health Organization

## **12. APPENDIX**

### **a. Hand Sanitizer Product Ingredients**

#### **i. Spectrum™ Advanced Hand Sanitizer Foam**

Ingredients (Active): 70% v/v Ethyl Alcohol

Ingredients (Inactive): (Alphabetical) denatonium benzoate, Glycerin, Glyceryl caprylate, Isopropyl myristate, PEG-12 dimethicone, t-butyl alcohol, Water

## b. Ecolab Foam Hand Sanitizer Study Design Bulletin

### Ecolab Foam Hand Sanitizers

#### PRODUCT USAGE RECOMMENDATIONS FOR ALCOHOL BASED HAND RUBS

In light of pending changes to the 1994 FDA Tentative Final Monograph (TFM) and requirements for Health Care Personnel Hand Wash/Rub, Ecolab has sought alternative guidelines for determining proper dosing of alcohol based hand sanitizers in health care environments. The Center for Disease Control and Prevention (CDC) and World Health Organization (WHO) indicate hands should remain wet for at least 15 seconds while being rubbed together after application of an alcohol-based hand rub. CDC and WHO guidelines further indicate the ideal volume of product to apply to the hands is not known, and may vary for different formulations. Ecolab testing has demonstrated on average 0.7 ml of *Quik-Care Foam Hand Sanitizer* (our fastest drying foam) is sufficient to keep hands wet for at least 15 seconds while being rubbed.

#### TEST METHOD

[figure not shown]
0.7ml of *Quik-Care Foam Hand Sanitizer* was dispensed onto one palm of the test subject. The test subject then rubbed his/her hands until dry. An observer using a stopwatch measured the time elapsed from when application began until the test subject indicated his/her hands felt dry. 42 test subjects participated in the study.

#### STUDY CONCLUSION

Under the conditions of this testing, 0.7 ml of *Quik-Care Foam Hand Sanitizer* was found to remain wet on the hands of a subject for an average of 17.1 seconds.

#### STUDY DISCUSSION

As indicated, CDC and WHO guidelines state the ideal volume of product to apply to the hands is not known, and may vary for different formulations. This study shows a minimum of 0.7ml of *Quik-Care Foam Hand Sanitizer* can be used to meet the CDC and WHO guidelines indicating hands should remain wet for at least 15 seconds during application of an alcohol-based hand sanitizer. Depending on configuration options, Ecolab Nexa foam dispensers output 0.7ml or 1.0ml of product; therefore, for most people, 1 pump from an Ecolab Nexa foam dispenser delivers enough product to meet the CDC and WHO guidelines on product volume usage.

Ecolab continues to partner with industry and regulatory bodies to navigate the changing landscape for soap and sanitizer use in health care environments.

 Centers for Disease Control and Prevention. Guideline for Hand Hygiene in Health-Care Settings: Recommendations of the Healthcare Infection Control Practices Advisory Committee and the HICPAC/SHEA/APIC/IDSA Hand Hygiene Task Force. MMWR 2002;51(No. RR- 16): 11, 13.

 World Health Organization (WHO). *WHO Guidelines on Hand Hygiene in Health Care*. Geneva: WHO, 2009

